c. Blinding, including justification for blinding or not blinding the trial, if applicable. N/A

d. Justification of why participants will not receive routine care or will have current therapy stopped.

There will be no effect on routine clinical care.

e. Justification for inclusion of a placebo or non-treatment group. N/A

f. Definition of treatment failure or participant removal criteria The participants will be removed from the study if they develop a clinically significant illness or a major bleeding complication attributed to apixaban (as opposed to minor issues, which need

not remove the participant from the study).

g. Description of what happens to participants receiving therapy when study ends or if a participant's participation in the study ends prematurely.

If the subject discontinues early, will we conduct an exit interview with final assessment.

5. Inclusion/Exclusion Criteria Inclusion Criteria:

- Men or women, 18 to 65 years old with a BMI of 35 kg/m² or greater who will be undergoing bariatric surgery (VSG and RYGB).
- Signed written informed consent
- Women of childbearing potential (WOCBP) must have a negative serum or urine pregnancy test (minimum sensitivity 25 IU/L or equivalent units of HCG) within 24 hours prior to the start of study drug.
- Women must not be breastfeeding

Exclusion Criteria:

- History of documented clotting/coagulation disorder.
- History of cancer (within the last year)
- Any diagnosis requiring anti-coagulation
- History of hypersensitivity reaction to apixaban
- Active clinically significant bleeding
- GFR < 30
- Participant who has moderate-severe liver disease (Child-Pugh B or C)

- Participants currently receiving any type of anticoagulation or blood thinning medications, including heparin, low molecular weight heparins, Plavix, aspirin, NSAIDS
- Participant who is taking any of the excluded medications (see Table 2 above)

6. Drugs/ Substances/ Devices

a. The rationale for choosing the drug and dose or for choosing the device to be used.

Drug procurement, handling, accountability and destruction will be carried out by the Johns Hopkins Bayview Research Pharmacy. Administration of the drug will be completed by nursing staff in the CRU. These nurses will be trained and familiar with the protocol.

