related" or "probably related" to the administration of apixaban. In such a case, we will not resume the study until the investigators, the sponsor, and the IRB are satisfied that there are alternative explanations for the events not related to apixaban, or the study procedures are altered to reduce the risk of such events for future participants. After the first 20 subjects, if there is ever a point where 10% or more of the subjects suffer a serious adverse event either "definitely" or "probably" related to apixaban, the same approach will be taken.

8. Risks

a. Medical risks, listing all procedures, their major and minor risks and expected frequency.

The only risks related to pharmacokintectic and pharmacodynamics studies are minor bleeding and/or bruising at the IV insertion site and the possibility of vasovagal reactions to blood draws.

The risks associated with use of apixaban are as follows:

Bleeding: As with other anticoagulants, subjects administered with apixaban are to be carefully observed for signs of bleeding.

Stroke: Stroke has been reported occasionally in studies of apixaban (multiple dosing studies). However, given that this is a single dose study – the likelihood of such a complication is rare. As part of good clinical practice, the investigators will remain vigilant.

b. Steps taken to minimize the risks.

To minimize the risks we will use experienced phlebotomists from the CRU to place the venous catheters for blood drawing or to draw the blood via venipuncture if preferred by the subject. Those drawing the blood will be familiar with the possibility of vasovagal reactions, and will have the subject lay down with legs elevated if the subject becomes symptomatic. The patients will be monitored for a full 24 hours after ingesting the single dose of apixaban. The participant will then return at 48 hours and at 72 hours at which time we can check in with the patient and ensure there are no side effects to the medication or complications. We will also closely monitor subjects before, during, and after study visits.

All records will be secured in research offices. Computers that contain patient data are password protected.

WOMEN OF CHILD-BEARING POTENTIAL (WOCBP)

Sexually active Women of Child-Bearing Potential (WOCBP) must use an effective method of birth control during the course of the study, in a manner such that risk of failure is minimized.

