Before study enrollment, WOCBP must be advised of the importance of avoiding pregnancy during study participation and the potential risk factors for an unintentional pregnancy. The subject must sign an informed consent form documenting this discussion.

All WOCBP MUST have a negative pregnancy test within 24hours before receiving apixaban. The minimum sensitivity of the pregnancy test must be 25 IU/L or equivalent units of HCG. If the pregnancy test is positive, the subject must not receive apixaban and must not be enrolled in the study.

In addition, all WOCBP should be instructed to contact the investigator immediately if they suspect they might be pregnant (e.g., missed or late menstrual period) at any time during study participation.

ADVERSE EVENT REPORTING

All Serious Adverse Events (SAEs) that occur following the subject's written consent to participate in the study through 30 days of discontinuation of dosing must be reported to Bristol Meyers Squibb (BMS) Worldwide Safety.

Adverse Events

- An Adverse Event [AE] is defined as any new untoward medical occurrence or worsening of a pre-existing medical condition in a patient or clinical investigation subject administered an investigational (medicinal) product and that does not necessarily have a causal relationship with this treatment. An AE can therefore be any unfavorable and unintended sign (including an abnormal laboratory finding, for example), symptom, or disease temporally associated with the use of investigational product, whether or not considered related to the investigational product.
- The causal relationship to study drug is determined by a physician and should be used to assess all adverse events (AEs). The causal relationship can be one of the following:
 - Related: There is a reasonable causal relationship between study drug administration and the AE.
 - Not Related: There is not a reasonable causal relationship between study drug administration and the AE.
- The term "reasonable causal relationship" means there is evidence to suggest a causal relationship.
- Adverse events can be spontaneously reported or elicited during open-ended questioning, examination, or evaluation of a subject. (In order to prevent reporting bias, subjects should not be questioned regarding the specific occurrence of one or more adverse events).

Serious Adverse Events

A Serious Adverse Event (SAE) is any untoward medical occurrence at any dose that:

- results in death

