- is life-threatening (defined as an event in which the subject was at risk of death at the time of the event; it does not refer to an event which hypothetically might have caused death if it were more severe)

- requires inpatient hospitalization or causes prolongation of existing hospitalization (see **NOTE***: below for exceptions)
- results in persistent or significant disability/incapacity
- is a congenital anomaly/birth defect
- is an important medical event, defined as a medical event that may not be immediately lifethreatening or result in death or hospitalization but, based on appropriate medical and scientific judgment, may jeopardize the subject or may require intervention (e.g., medical, surgical) to prevent one of the other serious outcomes listed above. Examples of such events include but are not limited to intensive treatment in an emergency department or at home for allergic bronchospasm; blood dyscrasias or convulsions that do not result in hospitalization.
- Suspected transmission of an infectious agent (eg, pathogenic or non-pathogenic) via the study drug is an SAE.

Although pregnancy, overdose, and cancer are not always serious by regulatory definition, these events must be handled as SAEs.

Adverse Events of Special Interest

In this study, the following adverse events are to be reported to BMS, regardless of whether these reports are classified as serious or unexpected.

- Potential or suspectived cases of liver injury including but not limited to liver test abnormalities, jaundice, hepatitis or cholestasis.

***NOTE:** The following hospitalizations are not considered SAEs:

- A visit to the emergency room or other hospital department lasting less than 24 hours that does not result in admission (unless considered an "important medical event" or a life-threatening event)
- Elective surgery planned before signing consent
- Admissions as per protocol for a planned medical/surgical procedure
- Routine health assessment requiring admission for baseline/trending of health status (eg, routine colonoscopy)
- Medical/surgical admission other than remedying ill health state that was planned before study entry. Appropriate documentation is required in these cases
- Admission encountered for another life circumstance that carries no bearing on health status and requires no medical/surgical intervention (eg, lack of housing, economic inadequacy, caregiver respite, family circumstances, administrative reason)

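### Bleeding is the first apixaban risk named, but staff may not ask about any specific adverse event, so non-serious bleeding after discharge may be under-ascertained

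*Combined protocol and SAP*

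**What the plan says.** Section 8a (medical risks) lists bleeding, then stroke, as the risks of apixaban. On bleeding it says that "subjects administered with apixaban are to be carefully observed for signs of bleeding".

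Section 4f (participant removal) removes a participant for clinically significant illness or for "a major bleeding complication attributed to apixaban (as opposed to minor issues", and adds that minor issues need not lead to removal. Neither major nor minor is defined.

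The Adverse Events subsection under section 8b gives the permitted ways of finding events: "Adverse events can be spontaneously reported or elicited during open-ended questioning, examination, or evaluation of a subject". It then says, with prevention of reporting bias as the reason, that "subjects should not be questioned regarding the specific occurrence of one or more adverse events". Bleeding is not excepted.

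On observation, section 8b states that "The patients will be monitored for a full 24 hours after ingesting the single dose of apixaban". Participants then come back to the unit for blood draws at 48 and 72 hours, when staff check for side effects and complications. There is also a general undertaking to monitor closely around visits. Table 1 schedules one adverse event review, the exit interview two weeks after the final visit, which section 10 describes as a telephone contact.

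On reporting, SAEs go to the company within 24 hours, and doubt about seriousness is to be resolved by filing an SAE report. Non-serious events are collected from the start of study drug and reach the company in annual (if applicable), interim or final reports. Under Adverse Events of Special Interest, "the following adverse events are to be reported to BMS, regardless of whether these reports are classified as serious or unexpected", and the only entry is "Potential or suspectived cases of liver injury including but not limited to liver test abnormalities, jaundice, hepatitis or cholestasis".

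**The concern.** Two instructions pull against each other. One asks for careful observation for bleeding. The other tells the same staff not to ask about any specific event, which on its face includes bleeding. While the participant is in the unit, observation can supply much of what is needed. After discharge, some bleeding leaves no sign on examination, and dark stools and heavy menses are examples. For these, the participant's account is the source, and staff may seek it only through an open question.

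What is at stake is the completeness of the non-serious bleeding record for an anticoagulant given three times after gastrointestinal surgery. There is a further, smaller issue. Section 4f asks the investigator to separate a major bleed from minor issues, and that judgement needs detail about the bleed that an open question may not bring out.

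**Working it through.** The plan states no figure on this point, so the check sets the passages side by side. Arithmetic is used only for timing and exposure.

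**Step 1: what each passage governs.**
- Section 8a: a duty to observe for bleeding.
- Section 8b, Adverse Events: how events may be found (spontaneous report, open questions, examination, evaluation), with questions about specific events barred.
- Section 8b, Adverse Events of Special Interest: what is sent to the company regardless of seriousness. It says nothing about how the site detects or records an event.
- Section 4f: a decision that uses the information once obtained.

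The conflict therefore lies between section 8a and the questioning rule in 8b, with section 4f as the user of the result. The special-interest list is not part of it.

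**Step 2: which bleeds are affected.**
- In the first 24 hours after a dose, the participant is an inpatient under monitoring, so the gap is small.
- Visible bleeding at the 48- and 72-hour draws can be found by examination, since both are visits in person.
- Bleeding not visible on examination, from discharge onwards, is found only if volunteered or raised by an open question.
- Serious bleeding goes by the 24-hour SAE route once known, and doubt about seriousness also leads there.

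The gap is thus non-serious bleeding that examination does not show, from hour 24 on.

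**Step 3: time not under inpatient observation.**
- Within the sampling period: 72 − 24 = 48 hours per dose.
- Dose 1 to dose 2, from the Table 1 windows: 3 + 4 = 7 weeks to 5 + 6 = 11 weeks, with surgery in between. Less the 3 days of sampling, 49 − 3 = 46 to 77 − 3 = 74 days have no safety contact scheduled in Table 1.
- Dose 2 to dose 3: 6 months less 6 weeks (about 26 − 6 = 20 weeks) to 8 months less 4 weeks (about 35 − 4 = 31 weeks).
- Dose 3 to dose 4: 12 − 8 = 4 months to 14 − 6 = 8 months.

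**Step 4: exposure.** With 15 per group and nobody lost, 30 × 4 = 120 doses, of which 30 × 3 = 90 are post-operative. Section 7c allows for 5 losses per group. If all 10 left after the first dose (an assumption), there would be 30 + 20 × 3 = 90 doses, 60 of them post-operative. These numbers count opportunities for a bleed to go unrecorded. They do not estimate missed bleeds, and the documents give neither a bleeding rate nor an under-reporting rate.

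**The case against.** The case for leaving the text alone has real force.

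- **The plan has several safeguards.** It provides inpatient monitoring, two check-ins in person, examination, open questions, collection of non-serious events from first dose, and an exit review. This stands. It rules out the inference that bleeding after 24 hours is known only from what the participant says.
- **The special-interest list concerns reporting.** A reader might infer that leaving bleeding off it causes bleeds to be missed, or that prompt reporting is used up on liver injury. The documents support neither. The list determines what goes to the company, listing one event takes nothing from another, and no deadline is attached to it. The 24-hour route belongs to SAEs and remains open to serious bleeding.
- **A missed minor bleed would not change removal.** This stands as far as it goes, because section 4f says minor issues need not remove a participant. Doses are also at least 7 weeks apart, so scheduled post-dose observation ends well before the next dose. What remains is that sorting major from minor needs detail, and the text restricts how staff may obtain it.
- **The open-question rule is deliberate and has a stated reason.** It does, but reporting bias carries little weight here. Every participant takes the same open-label drug, and a fixed question set would be put identically to both surgical groups at every visit.
- **Clinical outcomes are not the study's purpose.** Sections 6c and 7 confirm this. It limits the importance of the point, but the duty to observe for bleeding in section 8a still applies.

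**Conclusion.** The point holds in a limited form. Followed as written, the adverse event text restricts staff to open questions about the drug's first named risk, while section 8a asks for careful observation and section 4f relies on distinguishing major from minor bleeding. Non-serious bleeding that examination does not show may be under-ascertained from hour 24 after each dose, at the 48- and 72-hour check-ins and at later visits. The setting is up to 120 doses, 90 of them post-operative. The number of bleeds affected cannot be derived from the documents.

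This rests on two assumptions: that staff apply the bar literally, and that an open question brings out less than a direct one for bleeding that cannot be seen. The documents do not quantify the second.

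A reader might go further and infer a threat to the PK/PD results, or wrong decisions before the next dose. Neither is shown. The outcomes in section 7 are pharmacokinetic and pharmacodynamic, and serious bleeds remain covered by SAE reporting. The point is worth acting on because the correction is cheap.

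**What to change.** Reconcile sections 4f, 8a and the Adverse Events text under 8b as follows.

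1. Exempt bleeding from the bar on questions about specific events. Leave the bar in place for everything else.
2. Put the same short, fixed set of bleeding questions to every participant at contacts already planned: 24, 48 and 72 hours after each dose, the start of each later dosing visit, and the exit interview.
3. Record the answers as solicited events, tabulated apart from unsolicited adverse events. Keep expected bruising or minor bleeding at the venipuncture site separate, since section 8a already anticipates it and 13 samples per dosing visit could otherwise swamp the record.
4. Make sure the record holds the detail that section 4f's distinction needs. How major and minor are defined is for the investigators to settle.

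Adding bleeding to the events of special interest is optional and would change only what is reported to the company.

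The cost is a wording amendment and a few questions at 4 × 3 + 3 + 1 = 16 contacts per participant, at most 30 × 16 = 480 in all, with no new visit or test. The downside is that more minor bleeds will be recorded, and that solicited counts will not be comparable with unsolicited adverse events in this study or elsewhere.
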